10.4 APPENDIX 4: CONTRACEPTIVE GUIDANCE AND COLLECTION OF PREGNANCY INFORMATION

DEFINITIONS:

Woman of childbearing potential (WOCBP)

A woman is considered fertile following menarche and until becoming postmenopausal unless permanently sterile (see below).

Women in the following categories are not considered WOCBP

1. Premenarchal.
2. Premenopausal female with 1 of the following:
 - Documented hysterectomy,
 - Documented bilateral salpingectomy,
 - Documented bilateral oophorectomy.

Note: Documentation can come from the site personnel's review of the participant's medical records, medical examination, or medical history interview.

3. Postmenopausal female

- A postmenopausal state is defined as no menses for 12 months without an alternative medical cause. A high follicle-stimulating hormone (FSH) level in the postmenopausal range may be used to confirm a postmenopausal state in women not using hormonal contraception or hormone replacement therapy (HRT). However, in the absence of 12 months of amenorrhea, a single FSH measurement is insufficient,
- Females on HRT and whose menopausal status is in doubt will be required to use one of the non-estrogen hormonal highly effective contraception methods if they wish to continue their HRT during the study. Otherwise, they must discontinue HRT to allow confirmation of postmenopausal status before study enrollment.

CONTRACEPTION GUIDANCE

Female participants

Female participants of childbearing potential are eligible to participate if they agree to use a highly effective method of contraception consistently and correctly as described in [Table 10](#).

In addition WOCBP must refrain from donating ova for the duration of the study and at least 5 weeks after last dose of IMP.

Table 10 - Highly effective contraceptive methods

Highly effective contraceptive methods that are user dependent^a

Failure rate of <1% per year when used consistently and correctly.

Combined (estrogen and progestogen containing) hormonal contraception associated with inhibition of ovulation

- Oral^b.
- Intravaginal.
- Transdermal.

Progestogen only hormonal contraception associated with inhibition of ovulation

- Oral^b.
- Injectable.

Highly effective methods that are user independent^a

- Implantable progestogen only hormonal contraception associated with inhibition of ovulation.
- Intrauterine device (IUD).
- Intrauterine hormone-releasing system (IUS).
- Bilateral tubal occlusion.

Vasectomized partner

A vasectomized partner is a highly effective contraception method provided that the partner is the sole male sexual partner of the WOCBP and the absence of sperm has been confirmed. If not, an additional highly effective method of contraception should be used.

Sexual abstinence

Sexual abstinence is considered a highly effective method only if defined as refraining from heterosexual intercourse during the entire period of risk associated with the study intervention. The reliability of sexual abstinence needs to be evaluated in relation to the duration of the study and the preferred and usual lifestyle of the participant.

NOTES:

a Typical use failure rates may differ from those when used consistently and correctly. Use should be consistent with local regulations regarding the use of contraceptive methods for participants participating in clinical studies.

b Pharmacokinetic drug-interaction potential of oral hormonal contraception with the study treatment is low, but still unknown. Therefore, if the oral contraceptive cannot be replaced by other highly effective method of contraception, with different route of administration, the hormonal contraception method must be supplemented with a male condom (for partner) during the treatment period and for at least 5 weeks (ie, until Follow-up Visit 15) after the last dose of IMP.

PREGNANCY TESTING:

- WOCBP should only be included after a confirmed menstrual period and a negative highly sensitive serum pregnancy test.
- Additional pregnancy testing should be performed at each on-site visit during the treatment period, at the last study visit (6 weeks \pm 7 days after the last dose of study intervention), and as required locally.
- Pregnancy testing will be performed whenever a menstrual cycle is missed or when pregnancy is otherwise suspected.

COLLECTION OF PREGNANCY INFORMATION:

Male participants with partners who become pregnant:

- The Investigator will attempt to collect pregnancy information on any male participant's female partner who becomes pregnant while the male participant is in this study. This applies only to male participants who receive IMP.
- After obtaining the necessary signed informed consent from the pregnant female partner directly, the Investigator will record pregnancy information on the appropriate form and submit it to the Sponsor within 24 hours of learning of the partner's pregnancy. The female partner will also be followed to determine the outcome of the pregnancy. Information on the status of the mother and child will be forwarded to the Sponsor. Generally, the follow-up will be no longer than 6 to 8 weeks following the estimated delivery date. Any termination of the pregnancy will be reported regardless of fetal status (presence or absence of anomalies) or indication for the procedure.

[figure not shown]
Female participants who become pregnant:

- The Investigator will collect pregnancy information on any female participant who becomes pregnant while participating in this study. Information will be recorded on the appropriate form and submitted to the Sponsor within 24 hours of learning of a participant's pregnancy. The participant will be followed to determine the outcome of the pregnancy. The Investigator will collect follow-up information on the participant and the neonate and the information will be forwarded to the Sponsor. Generally, follow-up will not be required for longer than 6 to 8 weeks beyond the estimated delivery date. Any termination of pregnancy will be reported, regardless of fetal status (presence or absence of anomalies) or indication for the procedure.
- Any pregnancy complication or elective termination of a pregnancy will be reported as an AE or SAE. A spontaneous abortion is always considered to be an SAE and will be reported as such. Any poststudy pregnancy-related SAE considered reasonably related to the study intervention by the Investigator will be reported to the Sponsor as described in [Section 8.3.4](#). While the Investigator is not obligated to actively seek this information in former study participants, he/she may learn of an SAE through spontaneous reporting.
- Any female participant who becomes pregnant while participating in the study will discontinue study intervention.

10.5 APPENDIX 5: LIVER AND OTHER SAFETY: SUGGESTED ACTIONS AND FOLLOW-UP ASSESSMENTS

10.5.1 Laboratory abnormalities

[figure not shown]
NEUTROPENIA

* For individuals of African descent, the relevant value of concern is <1000/mm³

Neutropenia is to be recorded as an AE only if at least 1 of the criteria listed in the general guidelines for reporting AEs in Appendix 3 (Section 10.3) is met.

[figure not shown]
THROMBOCYTOPENIA

Note:

The procedures above flowchart are to be discussed with the patient only in case described in the the event occurs. If applicable (according to local regulations), an additional consent (e.g., for HIV testing) will only be obtained in the case the event actually occurs.

Thrombocytopenia is to be recorded as an AE only if at least 1 of the criteria listed in the general guidelines for reporting AEs in Appendix 3 ([Section 10.3](#)) is met.

[figure not shown]

*If unable to retest in 72 hours, use original lab results to decide on further reporting/monitoring/discontinuation.

Note:

[figure not shown]
- “Baseline” refers to ALT sampled at baseline visit; or if baseline value unavailable, to the latest ALT sampled before the baseline visit. The algorithm does not apply to the instances of increase in ALT during screening.
- See [Section 8.3](#) for guidance on safety reporting.
- Normalization is defined as \leq ULN or baseline value, if baseline value is $>$ ULN.

INCREASE IN SERUM CREATININE

Increase in serum creatinine is to be recorded as an AE only if at least 1 of the criteria listed in the general guidelines for reporting AEs in Appendix 3 ([Section 10.3](#)) is met.

**INCREASE IN CPK SUSPECTED TO BE OF NON-CARDIAC ORIGIN
AND NOT RELATED TO INTENSIVE PHYSICAL ACTIVITY**

Increase in creatine phosphokinase is to be recorded as an AE only if at least 1 of the criteria in the general guidelines for reporting AEs in Appendix 3 ([Section 10.3](#)) is met.

10.5.2 Monitoring of participants with increased lipase and/or amylase $>2 \times \text{ULN}$

GLP-1 RAs stimulate pancreatic beta-cell and suppress alpha-cell function. Some cases of acute pancreatitis have been reported with marketed GLP-1 RAs. Therefore, participants enrolled in this study should be closely monitored for any suspected pancreatitis, eg, with symptoms and/or signs of acute abdominal distress or abnormal levels of pancreatic enzymes. Serum amylase and lipase concentrations are monitored routinely at screening, baseline, and periodically during the study intervention period.

In the presence of clinical signs and/or symptoms evocative of pancreatitis, eg, persistent abdominal pain, which can radiate to the back, often with characteristic positional features, with possible occurrence of nausea, vomiting, fever, and leukocytosis, further measurement of amylase and lipase should be performed. The clinical signs and/or symptoms should be documented in the source data documentation.

Refer to [Section 10.5.2.1](#) and [Section 10.5.2.2](#) below for actions to take in case of elevation of amylase and/or lipase with or without clinical signs and/or symptoms evocative of pancreatitis, respectively.

In any situation as described below, all laboratory or clinical documentations must be collected. If the retest result confirms lipase and/or amylase values are $>2 \times \text{ULN}$, the event must be reported in the eCRF on the specific AE form and the specific complementary forms, using the appropriate verbatim, eg, “increased amylase and/or lipase” in case of isolated enzyme elevation, “suspected pancreatitis” in the presence of clinical signs evocative of pancreatitis if the diagnosis is suspected but cannot be confirmed or excluded, and “pancreatitis” if the diagnosis has been confirmed.

10.5.2.1 Elevation of amylase and/or lipase $>2 \times \text{ULN}$ without clinical signs and/or symptoms

In any case where amylase and/or lipase are $>2 \times \text{ULN}$, a retest (centrally assessed as far as possible) must be performed as follows:

- If value(s) is/are >2 to $3 \times \text{ULN}$ in a participant with baseline amylase and/or lipase values $<2 \times \text{ULN}$: retest within 7 days.
- If value(s) is/are $>3 \times \text{ULN}$: retest within 48 hours, regardless of baseline amylase and/or lipase values.
- If the value(s) remain(s) $>2 \times \text{ULN}$ upon retesting: amylase and/or lipase levels should be retested weekly until values are $<2 \times \text{ULN}$.

In case a retest is $>2 \times \text{ULN}$ a gastroenterological evaluation and imaging (ultrasound and/or computed tomography [CT] or magnetic resonance imaging [MRI] with contrast, as appropriate) is highly recommended. The absence of clinical signs and/or symptoms should be documented in the source documents (if clinical signs and/or symptoms develop, please see [Section 10.5.2.2](#) below).

Best clinical judgment is to be used when interpreting elevated serum amylase and lipase levels in asymptomatic participants. Temporary discontinuation of the IMP may be considered in these cases if deemed necessary by the Investigator.

10.5.2.2 *Elevation of amylase and/or lipase >2 × ULN with clinical signs and/or symptoms.*

In the presence of clinical signs and/or symptoms evocative of pancreatitis (as previously described) associated with elevated amylase and/or lipase, treatment with the IMP should be promptly and at least temporarily discontinued pending further clinical evaluation and diagnosis confirmation. Clinical signs and/or symptoms are to be documented in the source data.

A laboratory determination of amylase and lipase must be obtained at the time of the event and again within 48 hours or earlier as clinically indicated. If the value(s) remain(s) $>2 \times$ ULN, then amylase and/or lipase levels should be retested as described in [Section 10.5.2.1](#), or more often if clinically indicated.

A gastroenterologic evaluation and imaging (ultrasound and/or CT or MRI with contrast, as appropriate) must be performed as clinically indicated and as per clinical practice and local guidelines. If a diagnosis of pancreatitis is confirmed, IMP should not be restarted and should be permanently discontinued.

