7.1.1 Permanent discontinuation

Permanent intervention discontinuation is any intervention discontinuation associated with the definitive decision from the Investigator not to re-expose the participant to the IMP at any time during the study, or from the participant not to be re-exposed to the IMP whatever the reason.

The participants may withdraw from treatment with IMP if they decide to do so, at any time, and irrespective of the reason. Participants should discuss stopping study treatment with the site before doing so in order that questions can be addressed, concomitant therapy can be adjusted if needed, and a follow-up assessment arranged. All efforts should be made to document the reasons for treatment discontinuation and this should be documented in the eCRF.

A participant should withdraw from treatment with IMP in case of the following:

- Intercurrent condition that requires discontinuation of IMP: eg, laboratory abnormalities (see decision tree and general guidance for the follow-up of laboratory abnormalities in Appendix 5 [[Section 10.5](#)]), diagnosis of acute pancreatitis confirmed by gastroenterologic evaluation and imaging, unless a clear cause unrelated to IMP is confirmed and the participant has recovered from pancreatitis (see Appendix 5 [[Section 10.5.2](#)]), or calcitonin value ≥ 50 pg/mL (see Appendix 5 [[Section 10.5.3](#)]).
- If, in the Investigator's opinion, continuation with the administration of IMP would be detrimental to the participant's well-being.
- Pregnancy (in female participants).
- Confirmed intolerance to the allocated dose of IMP.
- Any code breaking requested by the Investigator.
- At the specific request of the Sponsor.

As all randomly assigned participants, under treatment or not, will be included in the study data analyses, it is important to collect efficacy and safety data from all participants, during the entire 56 weeks of the study. Collection of Week 30 data is of highest importance as they are needed for primary endpoint analysis. A high rate of missing data could jeopardize robustness of efficacy and safety findings and should be avoided. Refer to the SoA ([Section 1.3](#)) for data to be collected at the time of intervention discontinuation and follow-up and for any further evaluations that need to be completed.

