7.1.2 Temporary discontinuation

Temporary intervention discontinuation corresponds to at least 1 (one) dose not administered to the participants.

All IMP discontinuation should initially be considered as temporary unless permanent discontinuation is mandated by the protocol (see [Section 7.1](#)), and the Investigator should make best effort to resume IMP treatment as early as practically possible. There is no defined limit to the duration of temporary discontinuation.

Temporary intervention discontinuation may be considered by the Investigator because of suspected AEs (including intolerance to IMP planned dose). For all temporary intervention discontinuations, duration should be recorded by the Investigator in the appropriate pages of the eCRF.

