7.1.2.1 Rechallenge

Re-initiation of intervention with the IMP will be done under close and appropriate clinical/and or laboratory monitoring once the Investigator will have considered according to his/her best medical judgment that it is safe for the participant to re-start the IMP. In case of IMP intolerance, a one-time rechallenge is recommended following temporary discontinuation before deciding to permanently discontinue the IMP. If a maximum of 2 consecutive doses are missed, the IMP can be restarted with the last dose given. In cases where 3 or more consecutive doses are missed, the titration should be re-initiated.

Participants who temporarily discontinue IMP should be reassessed at every visit to determine whether it is possible to safely resume IMP. If a decision has been made that the discontinuation is permanent, then the participant should be considered as permanently discontinued and the corresponding eCRF page should be completed. Please note that permanent discontinuation should be a last resort.

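### Section 7.1.1 exempts some recovered participants with confirmed pancreatitis from mandatory IMP withdrawal, but Section 10.5.2.2, which it cites, bars restart with no exception

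*Protocol*

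**What the plan says.** Protocol Section 7.1.1 opens its list of reasons with "A participant should withdraw from treatment with IMP in case of the following". One entry is a "diagnosis of acute pancreatitis confirmed by gastroenterologic evaluation and imaging". That entry carries a qualification, "unless a clear cause unrelated to IMP is confirmed and the participant has recovered from pancreatitis", and points to Appendix 5, Section 10.5.2.

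Section 10.5.2.2 covers raised amylase or lipase with clinical signs or symptoms. It first requires at least a temporary stop while the diagnosis is worked up. It ends: "If a diagnosis of pancreatitis is confirmed, IMP should not be restarted and should be permanently discontinued". It makes no distinction by cause or by recovery.

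Two other sections govern what follows a stop. Section 7.1.2 says "All IMP discontinuation should initially be considered as temporary unless permanent discontinuation is mandated by the protocol", refers to Section 7.1 for those mandated cases, and asks the Investigator to make every reasonable attempt to resume. Section 7.1.2.1 gives the route back: "Re-initiation of intervention with the IMP will be done under close and appropriate clinical/and or laboratory monitoring", once the Investigator judges it safe.

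**The concern.** Pancreatitis is a recognised event of the GLP-1 RA class (Protocol Sections 2.3 and 10.5.2). Pancreatic events are also on the list requiring specific monitoring, and they go to adjudication (Sections 8.3 and 10.1.4.2). Whether a participant is re-exposed after such an event should follow from one rule that every site reads in the same way.

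Here the section that sets out mandatory withdrawal contains an exemption, and the section it cites for detail does not. A site working from Section 7 and a site working from Appendix 5 could therefore handle the same clinical picture differently, each with protocol text in support. What is at stake is participant safety and consistent conduct of the trial.

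**Working it through.** No arithmetic applies. The point depends on no sample size, power, effect size or event count, and the protocol states no figure to reproduce. The check sets the current text of the sections side by side.

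**Inputs.**
1. Withdrawal rule and exemption: Section 7.1.1.
2. Restart rule after confirmation: Section 10.5.2.2.
3. Default status of a stop: Section 7.1.2.
4. Rechallenge route: Section 7.1.2.1.

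All four are in the body of the amended protocol. None is superseded wording from the summary of changes.

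**Does one case fall under both rules?** Yes. A participant with symptoms, raised enzymes, and acute pancreatitis confirmed by evaluation and imaging meets the trigger in Section 7.1.1 and the trigger in Section 10.5.2.2.

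**Outcome by case, once pancreatitis is confirmed.**

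| Case | Section 7 | Section 10.5.2.2 | Result |
|---|---|---|---|
| (a) No clear unrelated cause confirmed | Withdraw | No restart; permanent stop | Agree |
| (b) Unrelated cause confirmed, not yet recovered | Exemption not met; no support for restarting at that time | No restart; permanent stop | No conflict over restarting at that time |
| (c) Unrelated cause confirmed, recovered | Withdrawal not required; stop is temporary (7.1.2); rechallenge open (7.1.2.1) | No restart; permanent stop | Conflict |

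**What Section 7.1.1 does in case (c).** Its exemption lifts a requirement. It does not order a restart or expressly permit one. The restart route comes from Sections 7.1.2 and 7.1.2.1, which apply because Section 7.1.1 no longer mandates permanent discontinuation.

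**Does the cross-reference settle it?** No. Following the reference from Section 7.1.1 to Section 10.5.2 leads to a sentence without the exemption. If that sentence governs, the exemption in Section 7.1.1 has no effect. If the exemption governs, the sentence in Section 10.5.2.2 is too broad.

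**Does any other text set precedence?** None was found. Appendix 5 is headed "LIVER AND OTHER SAFETY: SUGGESTED ACTIONS AND FOLLOW-UP ASSESSMENTS", which could suggest that it yields to Section 7. However, Section 7.1.1 cites it for exactly this situation, and its sentence is categorical. Exclusion criterion E 04 separates past pancreatitis by cause for eligibility, so the exemption in Section 7.1.1 is not an obvious slip. That criterion does not address restarting IMP during the study.

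**The case against.** The strongest reply is that one course of action satisfies both pancreatitis rules. A site that stops IMP permanently in case (c) complies with Section 10.5.2.2 and breaches nothing in Section 7.1.1, which only says when withdrawal is required. A reader might infer that each section can be followed only by breaching the other; the text does not support that. Only restarting breaches a rule, the one in Section 10.5.2.2. Permanent stopping sits uneasily with the instruction in Section 7.1.2 to try to resume, but that instruction yields where the protocol mandates a permanent stop.

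A careful site would also follow the references from Section 7.1.2 to 7.1.1 to 10.5.2 and end at the stricter sentence, so divergence between sites is possible rather than likely. This stands, but it leaves an exemption in Section 7.1.1 that means nothing, and a site has no way to know that this was intended.

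A reader might also infer a material effect on the SAP table of TEAEs leading to treatment discontinuation. The documents do not support that. The affected group is a subset of a rare event, Investigators are blinded to arm (Protocol Section 6.3.1), and SAP Section 2.4.4 makes the safety analysis descriptive with no systematic testing planned. After early termination, SAP Section 1.6 also dropped the planned efficacy evaluations, so the dependence of the protocol's imputation model on IMP discontinuation before Week 30 no longer matters.

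**Conclusion.** The inconsistency is real but narrow. It concerns only participants with confirmed pancreatitis, a confirmed cause unrelated to IMP, and recovery. A reader might take it to cover restarting after any confirmed pancreatitis. It does not: the sections agree when no unrelated cause is confirmed, and neither supports restarting before recovery. Within the narrow group, Section 7 leaves re-exposure open and Appendix 5 rules it out, with no stated order of precedence.

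The number affected should be very small. The documents give no expected count. Section 2.2 puts past exposure to efpeglenatide at about 720 participants, and Section 2.3 reports no pancreatitis case with efpeglenatide up to its data cut-off. Exposure times are not given, so no rate can be derived. That the number will be small assumes that this study would resemble those earlier ones.

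The point rests on participant safety and on the clarity of the protocol, with no meaningful effect on the analysis. It takes no position on which clinical rule is right. Because the SAP records that the study was stopped early, the correction now serves mainly to put on record which rule applied and to prevent the mismatch being carried into other protocols that reuse the text.

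**What to change.** Reconcile Protocol Sections 7.1.1 and 10.5.2.2 so that both state the same restart rule after confirmed pancreatitis, with or without the exemption. The choice is the sponsor's. The cost is about one sentence in one of the two sections, with no new procedures or data.

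No SAP change is needed. The listing of events sent for adjudication (SAP Section 2.4.4.1, analysis of adjudicated events) already includes the action taken with IMP and the duration of exposure, so individual cases can be reviewed from the planned output.
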